4.1 Objectives

[figure not shown]
1. Determine risk factors for neonatal early-onset sepsis in Kampala, Uganda
2. Use machine learning techniques to create a risk stratification model for early-onset sepsis in Uganda
3. Explore relationship between culture-positive sepsis and clinical diagnostic features in Uganda using machine learning techniques, including association between level of training of clinician documented diagnosis and blood culture result
4. Validate the model from Uganda externally using an independent dataset from a neonatal population in Harare, Zimbabwe

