A blood culture will be taken from all neonatal participants at birth, prior to starting antibiotic treatment wherever safe to do so. The volume of blood taken for culture must be 1-2ml and will be verified by weighing blood culture bottles. Training will be provided to paediatric and study teams on blood culture sampling methods, including adequate cleaning of the skin prior to sampling. Feedback on sample volumes and contamination rates (see section 7.3 for definition) will be fed back to paediatric consultants, and additional staff training offered. Where sample is remaining after 3ml is added to the culture bottle, the excess will be retained as a blood spot sample for use in future ethically approved research, where the participant has consented to this.

The results of the microbiological tests will be communicated to the participant's clinical team in real time – see section 7.3.4 for further details. Clinician diagnosis of sepsis will be recorded where a clinician of registrar level or above has recorded a diagnosis of sepsis within 48 hours of birth. To reduce the subjectivity of this measure, GAIA level of certainty for a diagnosis of sepsis will also be assessed (35) and the level of diagnostic certainty recorded (1-5, as per GAIA criteria). Medical records are recorded on paper at Kawempe Hospital, before being coded into an electronic medical record by data clerks. PDF scans of medical records will be available where detailed review is required.

All participant data will be collected by trained study staff, and recorded into an online CRF hosted on REDCap, a secure web application. No patient identifiable data will be stored on the main REDCap database. See section 8.6 for further details of data management plans.

The postnatal information will be completed via a telephone call at 28 days post-delivery, made by study staff. Participants' contact number, a contact number for their partner, and a contact number for a second friend or family member will be taken at recruitment to minimise loss to follow up due to changes to mobile telephone number. Participant identity will be confirmed using three factors (date of birth, full name, address/village). The following information will be collected:

- Health status of mother and baby
- Any visits to medical care for the neonate
 - If attended or admitted to Kawempe hospitals, these electronic medical records will be reviewed by study staff

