7.3.4 Biological Sample Handling

Blood samples will be taken from each neonate for culture (1-2ml) into BACTEC blood culture bottles and stored at room temperature until arrival at the laboratory. Sample volume will be verified by weight, and samples will be labelled with the neonate's ID.

Samples will be processed at Makerere Microbiology Laboratories (College of American Pathologists accredited) within 12 hours of collection(43). Samples will be incubated for 36 hours. Any presumptive positive culture will be plated onto selective agar and identified by biochemical tests. Couriers will collect samples from study sites and transport them to the Medical and Molecular Laboratories (MML) at Makerere University; coverage is available at weekends and some evenings by request from study staff, so a courier will be arranged if a sample is taken more than 12 hours before the next scheduled courier collection.

Sample results will be classified and handled as follows:

- Positive result: known potential pathogenic bacteria

Using machine learning to model early-onset neonatal sepsis risk in Uganda (NeoRisk)

- Pathogens included as per GAIA neonatal infection outcome list of 'recognised pathogens'(35)
- Study staff will notify clinical team and participant's parents by telephone; written notification also to be provided from laboratory (either via electronic system or hard copy) as per routine care
- Contaminant: growth of species considered 'non pathogenic' by GAIA list
 - Review clinical notes to determine presence of risk factors for invasive disease as a result of a normally commensal/contaminant organism (e.g. indwelling venous catheters causing risk of coagulase negative staphylococcal sepsis)
 - If no risk factors, written notification provided to clinical team from laboratory as above
 - If presence of risk factors or uncertainty, study team to additionally contact clinical team via telephone to notify
- Negative result: no growth
 - Written notification provided to clinical team from laboratory as above

Specific written consent will be taken from participants to store any leftover samples for use in future ethically approved research.

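### Objective 3: culture results reported before 48 h can prompt clinician diagnoses that are then counted as agreeing with the culture, so the association may be inflated

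*Combined protocol and SAP*

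**What the plan says.** Section 5 (Study design and methods) provides for real-time feedback to the clinical team in Phase 1: "The results of the microbiological tests will be communicated". It also fixes the window for the clinical outcome, with birth as the reference point: "Clinician diagnosis of sepsis will be recorded where a clinician of registrar level or above has recorded a diagnosis of sepsis within 48 hours of".

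Section 7.3.4 gives the laboratory sequence. Samples are processed within 12 h of collection, then "Samples will be incubated for 36 hours". Presumptive positives are next plated and identified by biochemical tests, for which no duration is given. The three classes of result are handled differently:

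- **Positive.** The class is defined as "Positive result: known potential pathogenic bacteria", and for it "Study staff will notify clinical team and participant's parents by telephone", with written notice as well.
- **Contaminant.** Written notice goes to the clinical team. A telephone call is added if the infant has risk factors for invasive disease or there is uncertainty.
- **Negative.** Written notice only.

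On sampling time, section 5 says in one place that the culture is taken before antibiotics or within 48 h of birth, whichever is sooner, and in another that it is taken at birth.

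Objective 3 (section 4.1) relates culture-positive sepsis to clinical diagnostic features, including the "association between level of training of clinician documented diagnosis and blood culture result".

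I found no rule that the diagnosis must come before the result, no blinding of the diagnosing clinician, no planned comparison of the two times, and no sensitivity analysis on this point. Section 7.3.3 time-stamps the completion of each data form. That is not the time of a diagnosis or of a notification.

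**The concern.** Objective 3 asks how clinicians' diagnoses line up with the culture. That is informative only if the diagnosis was reached without knowing the culture. Every Phase 1 infant is cultured whether or not sepsis is suspected, so some positives may occur in infants whom no clinician had diagnosed. Those discordant infants carry much of the information. If a call reaches the clinical team inside the 48 h window and a diagnosis is then written, a missed case becomes an agreement.

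Clinician sensitivity and the diagnosis–culture association would then look better than unaided bedside judgement. If notification times are not recorded as the study runs, it may not be possible to tell later which diagnoses followed a result.

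**Working it through.** The plan gives no figure for the Objective 3 association, so there is nothing to reproduce. Two checks apply: whether a call can fall inside the window, and what it would do if it did.

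**1. Timing**

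Inputs: diagnosis window 48 h from birth (section 5); sampling age S, at birth or up to 48 h (section 5); time to processing T, up to 12 h (section 7.3.4); incubation time until the culture flags positive F, up to 36 h (section 7.3.4); identification time I, not stated, assumed 0 to 24 h.

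Age at call = S + T + F + I. A call by 48 h requires F ≤ 48 − S − T − I.

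The longest timings with sampling at birth give 0 + 12 + 36 = 48 h before any identification.

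| S (h) | T (h) | I (h, assumed) | Latest flag time F allowing a call by 48 h |
|---|---|---|---|
| 0 | 12 | 0 | 36 h |
| 0 | 12 | 12 | 24 h |
| 0 | 12 | 24 | 12 h |
| 0 | 2 | 24 | 22 h |
| 24 | 12 | 0 | 12 h |
| 24 | 12 | 12 | 0 h |
| 24 | 12 | 24 | not possible (−12 h) |

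With sampling at 48 h no overlap is possible. Overlap therefore needs early sampling together with an early flag, quick processing or quick identification. The plan gives no distribution of time to positivity, so the share of positives affected cannot be derived.

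**2. Size if overlap occurs**

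Up to 5% of 1600 infants are expected to be culture-positive (section 7.2.1): 1600 × 0.05 = 80 at most. Two quantities are assumptions with no source in the plan: s0, the share of positives diagnosed unaided, and q, the share of the remaining positives that are phoned and then diagnosed before 48 h.

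Apparent sensitivity: s1 = s0 + (1 − s0)q.

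If the diagnosis rate among the other infants is unchanged, it cancels, and the odds ratio is multiplied by [s1/(1 − s1)] ÷ [s0/(1 − s0)].

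Example: s0 = 0.50 and q = 0.25 give s1 = 0.50 + 0.50 × 0.25 = 0.625. The multiplier is (0.625/0.375) ÷ (0.50/0.50) = 1.67, and 80 × 0.50 × 0.25 = 10 infants move.

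| s0 (assumed) | q = 0 | q = 10% | q = 25% | q = 50% |
|---|---|---|---|---|
| 30% | 1.00 | 1.37 | 2.11 | 4.33 |
| 50% | 1.00 | 1.22 | 1.67 | 3.00 |
| 70% | 1.00 | 1.16 | 1.48 | 2.43 |

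At s0 = 50% the number of the 80 positives moved is 0, 4, 10 and 20.

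**3. The opposing path**

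Some contaminants are telephoned too. If that call prompts a diagnosis, it raises the diagnosis rate among infants not classed as positive, which lowers the odds ratio. The table holds that rate fixed and so leaves this out.

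**The case against.** The strongest objection is the timing. The positive class that is telephoned is defined by organism, so plating and identification appear to come first. On the longest timings the call then falls after 48 h, and late sampling rules out overlap altogether. This stands as a limit on how much feedback can occur. It does not remove the possibility: 12 h is a ceiling, a culture can flag before 36 h, and the plan does not say whether an early flag or Gram stain is passed on before identification.

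Second, the scope is narrow. Objective 3 is exploratory, the Phase 1 primary outcome is the culture itself, and clinical signs present before a call are not created by it. GAIA certainty is recorded alongside the diagnosis, though that does not remove feedback. This stands, and it confines the point to analyses that set clinician diagnosis against culture.

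Third, part of the remedy may already exist. Applying a 48 h limit requires some record of diagnosis time, and scanned notes are available for review. The CRF is not among the documents, so the time fields cannot be said to be absent. The notification time is the more doubtful of the two.

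A reader might also infer that positives arrive inside the window while negatives do not. The plan does not establish this. With an assumed 2 h to processing, a final negative is available at 0 + 2 + 36 = 38 h.

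**Conclusion.** The point holds as a possibility that the plan leaves open and should close. For cultures reported before 48 h, the Objective 3 association between clinician diagnosis and culture result may be inflated by feedback. The effect runs from none to material. At an assumed unaided sensitivity of 50%, the odds ratio is multiplied by 1.00 to 3.00 as the converted share of missed positives goes from 0 to 50%. Time to positivity, identification time, unaided sensitivity and the conversion share are all absent from the plan, so no single figure can be defended.

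Two stronger readings are tempting. One is that the association is inflated as a matter of fact; the plan's own longest timings are compatible with no overlap at all. The other is that the bias can run only upward; that holds for pathogen calls alone, because telephoned contaminants can pull the other way. Upward is the more likely net direction, but the documents do not settle it.

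The Phase 1 primary outcome is not affected.

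**What to change.** 1. Record the date and time of the first documented sepsis diagnosis and of any result notification, for pathogens and contaminants alike.
2. Wherever clinician diagnosis is compared with culture, add an analysis that removes post-notification diagnoses without giving the groups unequal follow-up. Either apply one cut-off age to all infants, set before results are normally reported, or restrict to pre-notification diagnoses as a sensitivity analysis beside the all-diagnoses result.
3. Report the number of diagnoses made after notification.
4. Reconcile the two statements in section 5 on when the culture is taken.

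The pre-notification restriction should not be the sole or main analysis. It stops counting at the call for positives while other infants keep the full 48 h, so a positive infant who would have been diagnosed independently after the call is scored as missed. That biases clinician sensitivity downward.

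Result reporting to clinicians stays as it is. The cost is two time fields and one extra analysis. An early common cut-off also drops some later, independent diagnoses.

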STUDY FLOW CHART	7
1. BACKGROUND	9
2. RATIONALE	10
3. THEORETICAL FRAMEWORK	10
4. RESEARCH QUESTION/AIM(S)	15
5. STUDY DESIGN/METHODS	16
6. STUDY SETTING	19
7. SAMPLE AND RECRUITMENT	20
8. ETHICAL AND REGULATORY COMPLIANCE	25
9. DISSEMINATION POLICY	28
10. REFERENCES	29
11. APPENDICES	34

ABBREVIATIONS

CI	Chief Investigator
CRF	Case Report Form
ICF	Informed Consent Form
ISF	Investigator Site File
NHS	National Health Service
NIHR	National Institute for Health Research
PI	Principal Investigator
REC	Research Ethics Committee
SGUL	St Georges, University of London
JRES	(St Georges) Joint Research and Enterprise Services
WHO	World Health Organisation
ROM	Rupture of membranes
EOS	Early onset sepsis
LOS	Late onset sepsis
PCR	Polymerase chain reaction
LRS	Low resource setting

KEY STUDY CONTACTS

Chief Investigator	
Principal Investigator (In-Country)	
Study Co-ordinator	
Sponsor	St George's, University of London
Funder(s)	CREATE (Africa Health Research Training Programme) Wellcome Trust
Key Protocol Contributors	

STUDY SUMMARY	
Study Title	Using machine learning to model early-onset neonatal sepsis risk in Uganda
Internal ref. no. (or short title)	NeoRisk
Study Design	Observational
Study Participants	Neonates born at ≥ 34 weeks' gestational age at Kawempe Hospital in Kampala, Uganda (Phase 1) or Sally Mugabe Central Hospital in Harare, Zimbabwe (Phase 3)
Planned Size of Sample (if applicable)	1600 (Phases 1+2), 900 (Phase 3)
Follow up duration (if applicable)	1 month post-delivery
Planned Study Period	September 2023-May 2024
Research Question/Aim(s)	
1. Determine antenatal and perinatal factors associated with early-onset neonatal sepsis in low-resource settings, as diagnosed by a blood culture or a senior clinician2. Measure the strength of association between the above factors and early-onset neonatal sepsis3. Combine the above risk factors into a risk stratification model for early-onset neonatal sepsis using machine learning techniques
FUNDING AND SUPPORT	
FUNDER(S)	FINANCIAL AND NON FINANCIAL SUPPORT GIVEN
CREATE PhD Programme	

ROLES AND RESPONSIBILITIES OF STUDY MANAGEMENT COMMITTEES/GROUPS & INDIVIDUALS

The study has been discussed with the Community Engagement team at Makerere University-Johns Hopkins University Research Collaboration in Kampala, Uganda, which works with clinical studies at Kawempe Hospital.

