Using machine learning to model early-onset neonatal sepsis risk in Uganda (NeoRisk)

- If attended elsewhere, the mother will be asked the reason for presenting, whether the neonate was admitted to hospital, the main diagnosis, and any treatments given.

Recruitment of the first 160 participants from labour ward (10% of the overall sample) will be treated as a pilot, and both recruitment and data will be reviewed at this point with particular attention to the following aspects:

- Demographic comparison between recruited women and the population attending Kawempe
- Data completion
- Volume of blood culture samples taken
- Loss to follow up rates
- Association between potential risk factors and clinical sepsis, or culture-positive sepsis

After this pilot analysis, the data collection instrument may be adjusted to be more concise if some risk factors appear to have no relationship with neonatal outcomes. Additionally, the recruitment strategy may be adjusted to include women attending antenatal clinics to improve the representativeness of the sample if the pilot sample is significantly different demographically to the general population of pregnant women attending the same study site antenatally. Finally, feedback and staff training will be given as needed to ensure optimal sample volumes and data completeness.

During Phase 1, two separate focus group discussions with 10 participants each will be held with staff from Kawempe Hospital. One discussion will be with senior clinicians, and one with junior clinicians and midwives. The focus groups will be held on site at Kawempe in English. Focus groups are being held in order to complement the quantitative results of this project by highlighting risk factors currently perceived as significant (which should then be a key part of analysis and results dissemination to confirm their usefulness), inform of current diagnostic difficulties to guide future work with the risk stratification model, and provide context for development and communication of the model to maximise its utility. The focus groups will address the following issues:

- Ascertain knowledge and awareness of neonatal sepsis
- Management of neonatal sepsis
- regarding risks and consequences of neonatal sepsis, and
- Current diagnostic strategies and their perceived strengths and difficulties
- Perceptions of neonatal sepsis and how this might affect diagnosis and treatment
- Recommendations to enhance the diagnosis and treatment of neonatal sepsis

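### Objective 3 relates the diagnosing clinician's training level to culture result, but the Phase 1 recording rule starts at registrar level and so cuts off the range of training level

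*Combined protocol and SAP*

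**What the plan says.** Objective 3 (Section 4.1) is to explore, in Uganda, how culture-positive sepsis relates to clinical diagnostic features. It expressly covers the "association between level of training of clinician documented diagnosis and blood culture result". Training level is therefore an explanatory variable, and culture result is what it is compared with.

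The Phase 1 description in Section 5 gives the capture rule: "Clinician diagnosis of sepsis will be recorded where a clinician of registrar level or above has recorded a diagnosis of sepsis". The entry must date from the first 48 hours after birth. The Study Summary takes the same line in its first aim, where sepsis is "as diagnosed by a blood culture or a senior clinician".

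Four other places bear on the question:

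- Section 5 adds a graded assessment of each diagnosis, with "the level of diagnostic certainty recorded (1-5, as per GAIA criteria").
- On source records, Section 5 says "PDF scans of medical records will be available where detailed review is required".
- On the Phase 1 focus groups, it says "One discussion will be with senior clinicians, and one with junior clinicians and midwives".
- The data analysis part of Section 5 plans logistic regression for risk factors of clinical and microbiological sepsis. It describes no analysis by clinician grade.

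**The concern.** An association with training level can be estimated only over the range of training levels that enters the data. The objective sets no lower limit on that range, but the recording rule sets one at registrar. Followed as written, the study could not say whether diagnoses made below registrar level agree better or worse with culture.

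This matters because Phase 1 is well suited to the question. Every neonate is cultured whether or not sepsis is suspected, so clinicians' diagnoses can be set against culture without selective testing. Phase 3 cannot stand in for it. Objective 3 is confined to Uganda. In Harare, cultures are taken only when available, and only in neonates judged at risk or showing signs; the outcome there is itself a senior diagnosis. Section 3 also acknowledges that an individual clinician's diagnosis is subjective, so variation by grade is a substantive question.

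**Working it through.** The plan attaches no figure to this objective, so there is nothing to reproduce. The check compares the passages.

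**Step 1. Apply the Section 5 rule to each kind of infant.**

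| Sepsis documented within 48 hours by | Recorded under the rule? | Use for Objective 3 |
|---|---|---|
| Registrar or above only | Yes | Usable, if grade is captured |
| Lower grade, then registrar or above | Yes | Infant kept through the senior entry; the rule does not call for the lower-grade entry |
| Lower grade only | No | None |
| Nobody | No | Same status as the row above, if no recorded diagnosis is coded as not diagnosed |

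At infant level the loss is the third row: infants whose diagnosis was never documented at registrar level or above within the window.

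**Step 2. Look for anything that widens the rule.** The Study Summary repeats the restriction to senior clinicians. The GAIA level grades certainty of the diagnosis, not the training of the person who made it. Junior clinicians and midwives appear only in a focus group, which is qualitative and not linked to individual culture results. Scanned notes exist and are used for completeness checks (Section 7.3.3), but no section plans to extract lower-grade diagnoses from them. No section names a field for the diagnosing clinician's grade.

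**Step 3. Size.** The documents do not give the number of infants diagnosed only below registrar level. What can be bounded is the information available to the objective. Section 7.2.1 plans 1600 neonates and a culture-positive rate of up to 5%, so 1600 × 0.05 = 80 culture-positive infants at most on the planning rate, across all diagnostic groups.

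**Step 4. Direction of effect on a diagnosed-versus-not-diagnosed contrast.** Assume that lower-grade-only infants are coded as not diagnosed, which the documents do not state. Let p_S, p_J and p_N be the culture-positive proportions among infants with a registrar-or-above diagnosis, a lower-grade-only diagnosis and no diagnosis by anyone. Let v be the lower-grade-only share of all diagnosed infants, and w their share of the infants coded not diagnosed.

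- Contrast under the rule: C1 = p_S − [w·p_J + (1 − w)·p_N]
- Contrast with all grades recorded: C2 = [v·p_J + (1 − v)·p_S] − p_N
- Difference: C1 − C2 = v·(p_S − p_J) − w·(p_J − p_N)

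If p_J equals p_N, the difference is v·(p_S − p_N). If p_J equals p_S, it is −w·(p_S − p_N). With p_S above p_N, the rule enlarges the contrast in the first case and shrinks it in the second. None of these quantities is in the documents, so the direction is unknown.

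**The case against.** The strongest reply is that Section 5 does not say diagnoses are recorded only from registrar level. The sentence can be read as defining one clinical-sepsis variable, and the wording of Objective 3 suggests that grade is meant to be captured. The CRF is not among the documents. The Section 3 table is not presented as exhaustive and part of it is unreadable in the public text, so a grade field cannot be ruled out. Source notes are retained, so lower-grade entries may be recoverable. These points stand as limits. They do not remove the conflict: the rule is the only one stated, nothing widens it, and a grade field alone would not bring back diagnoses that the rule leaves out.

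Four stronger readings are tempting, and the documents do not support them.

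- A reader might infer that the protocol promised a junior-versus-senior comparison. Objective 3 names no junior staff, and a contrast between registrars and more senior doctors would satisfy its wording.
- A reader might infer that the share of data lost equals the share of first diagnoses made by juniors. It does not: an infant first diagnosed by a junior is still recorded if a registrar or above documents sepsis within 48 hours. Neither share is given.
- A reader might infer that the rule must dilute the association. Step 4 of the working shows that the sign is undetermined, and an analysis confined to diagnosed infants uses no undiagnosed group at all.
- A reader might infer that the window should also move to the 72 hours by which Section 3 defines early-onset sepsis. That is a separate question, and the grade problem does not need it.

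**Conclusion.** The objective and the recording rule do not fit together and must be reconciled. On the plain reading of Section 5, the training-level variable is truncated at registrar. Infants diagnosed only by lower-grade staff have no recorded clinician diagnosis, and the analysis is limited to a contrast within registrar-and-above, provided grade is captured. Objective 3 is narrowed, not defeated.

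The number of infants affected cannot be estimated from the documents, and neither can the direction of any effect on a diagnosed-versus-not-diagnosed contrast. The conclusion rests on two assumptions: that the stated rule is the operative one, and that the CRF does not separately collect lower-grade diagnoses.

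The reach is limited. This is one clause of an exploratory objective. It does not affect the Phase 1 primary outcome (positive blood culture), the model built on it, the sample size or the Phase 3 validation.

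**What to change.** In the Phase 1 CRF, record every documented sepsis diagnosis within the existing window of 48 hours from birth, with the clinician's grade and the time of the entry. Keep registrar or above only as the definition of the clinician-diagnosed sepsis outcome. State in the data analysis part of Section 5 that Objective 3 will be analysed by grade across all recorded levels.

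If the sponsor intends only a comparison among registrars and more senior doctors, restate Objective 3 in those terms and confirm that grade is captured.

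The first option costs one or two extra fields, abstracted from notes that two staff members already check against scanned records (Section 7.3.3). The second costs a change of wording plus, if it is not already there, a field for grade. Neither changes the outcome definition, the sample size or clinical care.
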